6.1 Examination Risks

Possible risks and discomforts associated with ocular examinations include:

 Dilating drops or anesthetic drops may sting. They can cause an allergic reaction, or if contaminated, can cause an infection, but neither of these problems is very likely to occur. Dilating drops can also cause a sudden increase of pressure (acute glaucoma) in eyes that are already predisposed to develop this condition. There is little risk of glaucoma being triggered in this way, but if it is, treatment is available. The participant's intraocular pressure will be obtained at each ophthalmic examination to determine whether there is an increased risk of developing glaucoma.

- 2. Color fundus photographs involve a bright flash to take pictures of the retina. This brief flash may cause temporary discomfort, but does not damage the eye.
- 3. In rare instances, the cornea may be scratched during measurement of intraocular pressure or use of a fundoscopic contact lens. A corneal abrasion of this sort may be painful, but it will heal quickly with no lasting effects.
- 4. The fluorescein dye used in fluorescein angiography can make a participant's skin turn yellow for several hours. This yellow color is transient and usually disappears in one day. Because the dye undergoes renal excretion, the participant's urine will turn dark orange for up to 24 hours after the examination. The study team will educate the participant regarding this urine color change. Some participants may be slightly nauseated during the examination, but their nausea usually lasts only a few seconds. If the dye extravasates during the injection, the skin around the injection site may feel mildly uncomfortable or become yellow. The discomfort usually lasts only a few minutes, and the yellow color fades in a few days. There is a chance of ecchymosis at the site of injection and a remote possibility of cellulitis from the needle track. In rare cases, participants may have an allergic reaction to the dye. Treatment typically consists of an oral antihistamine medication, but may require intravenous antihistamine administration if the symptoms are severe. Very rarely (less than one in one million people), a participant experiences anaphylaxis. This would be treated immediately by trained personnel with medications or, if necessary, intubation.
- 5. OCT is a non-invasive test used to document and analyze retinal pathology and has no known medical risks.

Possible risks and discomforts associated with non-ocular examinations include:

- Blood draws can cause discomfort and bleeding/bruising at the site of venous puncture. There is a remote risk of fainting or local infection. If any of these conditions arise, they will be treated.
- 2. The medical/ophthalmic history, physical examination, vital sign testing and pregnancy testing entail no medical risk.

6.2 Potential Risks of E10030

The following safety data for intravitreal use of E10030 are drawn from the attached Investigator Brochure (v5.0, February 29, 2016), furnished by Ophthotech Corp. Based on animal studies, injection-related risks appear to be limited to the risks of any intravitreal injection. Specifically, vitreous hemorrhage, retinal detachment, cataract, lens capsule pigmentation, fibrosis and retinal dysplasia were observed in some animals in multiple injection studies. Post-injection ocular inflammation may also be a risk of E10030 injection, although this reaction appears to be species-specific and has not been noted in human clinical trials.

In beagle dogs, a single intravitreal injection of test article was associated with trace to 1+ cell transiently in some eyes in the 0.3 mg/eye, 1.0 mg/eye and 2.0 mg/eye dose groups. On pathologic examination of these eyes, the minimal inflammation noted microscopically at all dose levels was considered of little toxicological significance. These findings were not associated with major changes in retinal function, as assessed by electroretinography (ERG). No inflammatory reaction was noted in single dose testing of Dutch belted rabbits.

Repeat injection studies were done in Dutch belted rabbits. The animals received bilateral injections every two weeks for six weeks and experienced no drug-related adverse effects. Several rabbits in the study and control groups sustained injection-related effects, including retinal detachment, cataract, lens capsule pigmentation, fibrosis and retinal dysplasia.

Repeat E10030 injection studies were also done in beagle dogs. Like the animals in the single injection studies, intermittent vitreous cells (trace to 2+; suggestion of dose dependence) were detected. This was especially common in the group that was injected daily. Two animals also had anterior chamber cells. One dog that received E10030 at the 0.3 mg dose level developed marked ocular inflammation that was severe and persistent. Injection-related effects included vitreous hemorrhage in six eyes, of which four were in the control group. Three other eyes had retinal folds. One of these three was in the control group. ERG and histopathology studies revealed no E10030-related toxicity.

New Zealand white rabbits that received multiple E10030/ranibizumab combined injections exhibited a species-specific ocular inflammatory reaction. Clinical signs of ocular inflammation included vitreous opacities, debris and infiltrating cells, fibrin and debris on the lens capsule.

Inflammation was confirmed on histopathology. The incidence and severity of these findings tended to increase over time on study. The inflammation was attributed to the known immunogenicity of ranibizumab in rabbit eyes, and was not seen at the highest dose level of E10030 alone. No similar inflammation was seen in an identical study in beagle dogs. The maximum serum concentration of E10030 in the high intravitreal dose group (1.5 mg) was 41 ng/mL. In rat studies, IV dosing (0.1, 1, 10 or 100 mg of E10030/kg/day IV over 14 or 90 days) has been associated with significant perturbations of hematology and clinical chemistry parameters, especially in the high-dose groups. Rats were found to have decreased leukocyte, hemoglobin, platelet and reticulocyte counts after IV administration. Prothrombin time and activated partial thromboplastin time were significantly increased at times during the study. Globulin levels were decreased by the end of the study, and there was a corresponding increase in albumin/globulin ratios. In the high-dose groups, serum cholesterol, ALT, total protein and AST, ALP, triglycerides and total bilirubin concentrations were all significantly decreased. Reductions in serum concentrations ranged from approximately 30 to 70%. Serum calcium was slightly but significantly reduced. Glucose and blood urea nitrogen concentrations were significantly increased, by as much as 55 and 75%, respectively. Increased liver weights and decreased spleen weights were also observed, and the significance of these findings is unclear. In the 14-day study, histopathology findings in the high-dose animals consisted of minimal to marked infiltration of histiocytes (macrophages) in multiple organs including the liver, spleen, lymph nodes and kidneys. In the 90-day study, histopathology findings in the high-dose animals consisted of cellular vacuolation in numerous tissues, including liver, spleen and lymph nodes. A dose response was evident, with increased severity and frequency of findings occurring in the high-dose group versus the mid-dose group. These histopathologic findings may reflect stages in the drug clearance process.

No drug-specific adverse effects of E10030 have been identified in limited human use. The only serious AE in the phase 1 clinical trial of E10030 was new onset atrial fibrillation reported by a patient in the 0.3 mg dose group. The event was assessed as unrelated to study drugs or injection procedure. In the phase 1 clinical trial of E10030 and ranibizumab for choroidal neovascularization in age-related macular degeneration (n=23) (OPH1000), AEs were almost exclusively mild and related to the injection procedure. The most frequently occurring (\geq 3 subjects) AEs were all events that occurred in the study eye, including foreign body sensation in the eye, conjunctival

hemorrhage, eye irritation and punctate keratitis. The only other ocular AEs reported in the study eye of more than one patient were conjunctival edema, anterior chamber cells (trace) and myodesopsia (floaters) (each reported in two patients, 9%). In a phase 2b randomized, prospective, double-masked, controlled trial of 449 patients with subfoveal neovascular lesions secondary to AMD (OPH1001), combination investigational treatment with E10030 and ranibizumab was well tolerated. Patients received six monthly intravitreous injections of E10030 given in combination with ranibizumab. In this randomized, sham-controlled, multicenter study, 449 patients were randomly assigned in a 1:1:1 ratio to the following dose groups: E10030 0.3 mg/eye + ranibizumab 0.5 mg/eye, E10030 1.5 mg/eye + ranibizumab 0.5 mg/eye or E10030 sham + ranibizumab 0.5 mg/eye.

The most common ocular AEs were, as expected in intravitreal studies, related to the intravitreal preparation and injection procedure and not drug-related, e.g., conjunctival hemorrhage, punctate keratitis and eye pain. There were no events of endophthalmitis, retinal detachment, retinal tear or iatrogenic traumatic cataract after a total of 4,431 intravitreal injections (1,776 administrations of E10030 and 2,655 administrations of ranibizumab). As expected, the mean IOP increased after each intravitreal injection consistent with the volume effect. However, mean IOP in all arms returned to pre-injection level at the next visit, including at the end of the study. The systemic safety profile of E10030/ranibizumab was similar to that of ranibizumab alone. In the phase 2b trial above (OPH1001), the incidence of SAEs was similar among treatment arms. The percentage of subjects with at least one systemic SAE was 8.7% in the group getting E10030 0.3 mg + ranibizumab 0.5 mg; 5.9% in the group getting E10030 1.5 mg + ranibizumab 0.5 mg; and 7.4% in the group getting sham + ranibizumab 0.5 mg. Systemic exposure to E10030 following intravitreous injection is extremely low. Pharmacokinetic studies have been performed in rats, rabbits and dogs and are described in the Investigator Brochure, but the most meaningful data comes from a dose-escalating, multiple-dose phase 1 study involving 23 participants with exudative AMD involving three monthly injections of E10030 (0.03, 0.3, 1.5 and 3.0 mg) plus ranibizumab (0.5 mg). In this study, plasma levels of E10030 were measured at days 0, 1, 3 and 7 and at week 4 and 8. E10030 was detectable in all participants receiving 1.5 mg or 3.0 mg doses. The mean maximum plasma concentration was calculated to be 15.9 ng/mL for those receiving 1.5 mg and 34.4 ng/mL for those receiving 3.0 mg, with an estimated terminal half-life of 8-14 days. By comparison, in animal studies, vitreous levels of E10030 were consistently more

than 1000-fold higher than systemic values. Further information is contained in the Investigator Brochure.

After intravitreal injection, transient increases in intraocular pressure should be anticipated in the immediate post-injection time period. Subjects should be cautioned on the potential risks associated with intravitreal injection procedures, which include retinal detachment, traumatic cataract, vitreous hemorrhage and intraocular infection, particularly endophthalmitis.

Present cumulative experience in completed and ongoing human trials described in the Ophthotech Corp. Investigator Brochure involves use of E10030 in combination with an anti-VEGF agent (ranibizumab, bevacizumab or aflibercept) in approximately 1,245 subjects. To date, serious AEs have been reported in 225 participants, including four suspected unexpected serious adverse reactions: one case of uveitis in the OPH1001 trial; one case of cerebral hemorrhage in the OPH1002 trial; one case of retinal pigment epithelial tear in the OPH 1003 trial; and one case of left facial numbness with negative neurologic work-up, resolving within a day, in the OPH 1004 trial, none of which has been considered to be likely to be related to E10030 administration by the Sponsor. Only one other case of uveitis (not designated a suspected unexpected SAE by investigators) has been reported across existing studies to date.

No evidence was observed for a toxic or pharmacokinetic interaction between E10030 and the anti-VEGF agent ranibizumab when the combinations were administered by the intravitreal route to dogs and rabbits. Although no systematic studies of interactions have been conducted with other drugs to date, no interactions of E10030 with other drugs are anticipated. E10030 is metabolized by nucleases in vitreous humor and plasma; therefore, cytochrome P450- mediated drug interactions are unlikely.

To date, no specific studies have been conducted to assess the effects of E10030 on the reproductive ability of adult animals or developmental parameters of fetuses or pups; therefore, E10030 must not be used during pregnancy or lactation. All women of childbearing potential must use two forms of effective contraception.

6.3 Potential Risks of Ranibizumab

Ranibizumab (Lucentis®) is made by Genentech, Inc. and approved by the FDA as an intravitreal injection for the treatment of neovascular age-related macular degeneration, macular edema secondary to retinal vein occlusion, diabetic macular edema (DME) and diabetic retinopathy in people with DME. Ranibizumab may cause allergic reactions although, to date, none have been reported. Several thousand patients have been treated with ranibizumab for different therapeutic indications in clinical trials. Serious AEs possibly or probably attributed to intravitreal injection of ranibizumab include severe uveitis, endophthalmitis, retinal tears, retinal detachment, vitreous hemorrhage, lens damage and central retinal vein occlusion. Non-serious AEs possibly or probably attributed to intravitreal injection of ranibizumab include anterior chamber and vitreal inflammation, mild transient increases in IOP, posterior vitreal detachment, retinal hemorrhage, injection site pain, subconjunctival hemorrhage and transient decrease in visual acuity. Other ocular non-serious events included a foreign body sensation in the eye after intravitreal injection, conjunctivitis, dry eye and pruritus. Some of these ocular side effects may cause decreased vision and a possibility of causing blindness. Although there was a low rate of arterial thromboembolic events (ATEs) observed in the ranibizumab clinical trials, there is a potential risk of ATEs following intravitreal use of VEGF inhibitors. ATEs are defined as nonfatal stroke, nonfatal myocardial infarction or vascular death (including deaths of unknown cause).

The safety of ranibizumab in pregnant or lactating women has not been tested.

6.4 Potential Risks of Any Intravitreal Injection

Potential risks of any injection are related to the mechanics of manipulating the eye. Potential risks associated with intravitreal injection itself are similar to those associated with the injection of other approved drugs delivered via the same route and include endophthalmitis, retinal tear, retinal detachment, lens trauma, intraocular hemorrhage and elevated intraocular pressure. Such risks can lead to irreversible vision loss or blindness. These risks will be minimized by restricting performance of the treatment to clinicians with experience in intravitreal injection and by use of a standardized injection procedure. Appendix 3 describes the injection procedure that will be used.

7.0 PARTICIPANT SAFETY MONITORING

Participants will be assessed for AEs during all study visits by the study investigators. At each visit, the participant will be asked about any new ocular or systemic symptoms including hospitalizations or new/changed medications. Participants will be instructed to contact a study investigator at any time if they experience any problems.

Participants will be monitored at each visit for injection-related complications such as endophthalmitis, retinal tear/detachment, intraocular hemorrhage, cataract and glaucoma and for any progression of ocular VHL disease. They will also be monitored at each visit for intraocular inflammation (as assessed by presence of anterior chamber or vitreous cell on ophthalmoscopy), which was noted in some pre-clinical models using doses of E10030 higher than the human equivalent dose planned for this study.

7.1 Treatment of Endophthalmitis, Retinal Tear/Detachment, Intraocular Hemorrhage, Cataract and Glaucoma

The decision to treat a participant for endophthalmitis, suspected endophthalmitis, retinal tear/detachment, intraocular hemorrhage, cataract or glaucoma will be guided by the clinical judgment of the investigator. Clinical management is also at the discretion of the investigator and should follow current standard practice patterns. A decision regarding whether discontinuation of combination investigational treatment is warranted will be made by the investigator in consultation with the participant.

7.2 Individual Withdrawal Criteria

Participants may choose to withdraw from this study for any reason at any time without penalty, loss of benefits or prohibition from enrolling in other clinical protocols. Reasons for participant discontinuation of combination investigational product or withdrawal may include, but are not limited to, the following:

- Visual acuity loss of \geq 30 letters from baseline;
- Investigator determination that it is not in the best medical interest of the participant to continue participation;
- Findings in the course of the trial that may affect willingness to participate;

- Inability to keep study visits or to comply with study requirements;
- Participant requires ocular surgery which cannot safely be postponed until the end of the study;
- Pregnancy;
- An adverse reaction to the study treatment or a serious complication associated with or aggravated by continuation of one or both investigational products;
- Cardiovascular event or stroke; or
- Other safety concerns.

Discontinuation of the combination investigational treatment does not necessitate study withdrawal. Whenever possible, investigators will ask study participants discontinuing combination investigational treatment to continue to return for study visits.

7.3 **Pregnancy Monitoring**

If an investigator becomes aware that a female study participant has become pregnant during the study, no further intravitreal injections of combination investigational treatment will be administered. The investigator and participant will determine whether to continue any remaining study visits or to exit the study.

If an investigator becomes aware that a male study participant has impregnated his partner during the study, the investigator will remind the participant of the potential risks to the unborn fetus.

In either case of reported pregnancy, participant (or partner) will be referred to the NIH OB/GYN consultation service for evaluation and counseling. The investigator must follow the participant (or partner) until the pregnancy outcome.

8.0 OUTCOME MEASURES

8.1 **Primary Outcome**

The primary outcome for the study will be safety of the combination investigational treatment, assessed by tabulation of AEs reported through Week 52.
8.2 Secondary Outcomes

Secondary outcomes will include tabulation of AEs reported through Week 104 and the following measures in the study eye at Week 52 and 104: the proportion of participants experiencing reduction in size of at least one RCH in the absence of other ablative treatment (assessed by fundus photography and FA); the proportion of participants experiencing moderate vision loss (defined as a loss of \geq 15 letters from baseline on EVA testing); mean change in visual acuity; change in size of RCH (measured by fundus photography and FA); change in epiretinal proliferation, fibrosis or retinal traction (assessed by OCT and fundus photography); proportion of participants undergoing ablative treatment of RCH or ocular surgery; proportion of participants with successful ablative treatment of RCH; and the proportion of participants with appearance of one or more new RCH.

9.0 STATISTICAL ANALYSIS

All participants will be included in the analyses.

9.1 Primary Outcome Analysis

In this open-label, prospective study, analyses will be primarily descriptive and by participant. All ocular and systemic AEs reported through Week 52 will be tabulated by participant. AE frequencies will be presented by body system, severity and whether they are considered related to the study treatment.

9.2 Secondary Outcome Analysis

The proportion of participants experiencing reduction in size of at least one RCH, in the absence of other ablative treatment, will be assessed by fundus photography and FA images taken at Week 52 and 104 compared to baseline. OCT, fundus photograph and FA findings will be presented by participant to indicate increases/decreases in lesion size and exudation from baseline. Change in epiretinal proliferation, fibrosis or retinal traction will be assessed by fundus photography and OCT and will be reported descriptively for each participant. The proportion of participants experiencing moderate vision loss (defined as a loss of ≥ 15 letters from baseline on EVA testing); undergoing ablative treatment of RCH or ocular surgery; achieving successful

ablative treatment of RCH; and showing appearance of one or more new RCH in the study eye will be reported. Mean change in visual acuity will be tabulated.

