4.5 Ocular and Systemic Evaluations

- 1. Medical/Ophthalmic History
- 2. Concomitant Medications Assessment
- 3. Vital Signs
- 4. Physical Examination
- 5. AE Assessment
- 6. Best-corrected visual acuity (BCVA) and Manifest Refraction using EVA Method

- 7. Slit Lamp Examination
- 8. Dilated Fundus Examination
- 9. Intraocular Pressure (IOP)
- 10. Color Fundus Photography
- 11. Optical Coherence Tomography (OCT)
- 12. Fluorescein Angiography (FA)
- 13. Complete Blood Count with Differential (CBC)
- 14. Acute Care Panel
- 15. Hepatic Panel
- 16. Mineral Panel
- 17. Hemoglobin A1C
- 18. Pregnancy Test (for women of childbearing potential as defined in Appendix 1)

It is expected that tests at any given visit can be completed in one day. The testing schedule varies with the visit. The evaluation and testing schedule is outlined in the study flowsheet (Appendix 2).

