4.5.1 Reporting of Expected Events

It is anticipated that participants in this study will occasionally miss or fail to complete an assessment, procedure, or study visit. These omissions will be considered expected events and not protocol deviations provided they are infrequent and do not include data needed to assess safety or the primary study outcome. If such an event is identified, the PI will submit a report to the IRB within two weeks using PTMS.

Cumulative proportions of these missed events in the study population will be presented to the IRB annually. In addition, these rates will be calculated and provided to the NEI SAE Review Committee regularly. The following are considered deviations:

- An individual misses more than 15% of the required study assessments/procedures,
- An individual misses more than 15% of the required study visits,
- An individual completes more than 15% of the required study visits outside of the visit window,

- Collectively, participants missed more than 15% of a specific assessment/procedure,
- Collectively, participants missed more than 15% of the required study visits, or
- Collectively, participants complete more than 15% of the required visits outside the visit window.

If total number of items (study visits or study assessments/procedures) expected is less than 16, two or more missed is reportable. If the total number expected is greater than 16, then if more than 15% are missed it is reportable. Missed items previously reported are not included in the subsequent tallies of missed items, but will be mentioned in future deviation reports. Once a deviation is identified, the PI will submit a report to the IRB within two weeks using PTMS.

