APPENDIX 2: STUDY FLOWSHEET

- * All visits during the first year must be conducted within a window of ±7 days from the target visit day. After Week 52, visits are conducted within a window of ±30 days from the target visit day.
- ¹ Manifest refraction must be performed when scheduled and when there is a change in visual acuity of ≥ 10 E-ETDRS letters ($\geq 0.20 \log MAR$) as compared with testing at the last visit.

- ² These procedures may be completed under another NEI/NCI/NINDS protocol if performed within 31 days prior to the baseline visit.
- ³ Only for women of childbearing potential. See Appendix 1 for guidance on determining whether a female is considered to be of childbearing potential. Some women may require a follicle-stimulating hormone (FSH) test to determine childbearing potential. Participants who meet this definition must have a negative test within 24 hours prior to injection of any investigational product.

Visit Schedule*	(Y2 Extra ^{**})	60	72	84	104
Visit Number (week)	N/A	060	072	084	104
Target Day From Baseline	N/A	420	504	588	728
GENERAL ASSESSMENTS					
Medical/Ophthalmic History					
Concomitant Medications Assessment	Х	Х	Х	Х	Х
Vital Signs		Х	Х	Х	Х
Physical Examination					
Adverse Event Assessment	Х	Х	Х	Х	Х
OCULAR ASSESSMENTS (BOTH EYES)					
BCVA (EVA)	Х	Х	Х	Х	Х
Manifest Refraction ¹					
Slit Lamp Examination	Х	Х	Х	Х	Х
Dilated Fundus Examination	Х	Х	Х	Х	Х
Intraocular Pressure (IOP)	Х	Х	Х	Х	Х
Color Fundus Photography					
Optical Coherence Tomography (OCT)	Х	Х	Х	Х	Х
Fluorescein Angiography (FA)					
LABORATORY		_	-	_	
Complete Blood Count (CBC)					
Acute Care Panel					
Hepatic Panel					
Mineral Panel					
Hemoglobin A1C					

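### Are the Week 104 tumor-size outcomes left without the fundus photographs and angiograms they depend on?

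*Protocol*

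**What the plan says.** Protocol 8.2 lists, at Weeks 52 and 104, the proportion of participants with reduction of at least one RCH and "change in size of RCH (measured by fundus photography and FA"). Protocol 9.2 adds that the first of these "will be assessed by fundus photography and FA images taken at Week 52 and 104 compared to baseline", and that "OCT, fundus photograph and FA findings will be presented by participant to indicate increases/decreases in lesion size and exudation from baseline". SAP 3.5.2 and 8.2 repeat both time points and both modalities, and SAP Table 7 has a full set of Week 104 columns.

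Visit-level timing is left to the flowsheet. Protocol 4.5 states: "The evaluation and testing schedule is outlined in the study flowsheet (Appendix 2"). The year-1 table of Appendix 2 marks photography and FA at baseline, Week 16 and Week 52. In the extension table, the rows "Color Fundus Photography" and "Fluorescein Angiography (FA") appear with no mark in any column, while optical coherence tomography (OCT) is marked at every visit, including Week 104.

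**The concern.** A secondary outcome is defined by images at Week 104, and the table that schedules the images appears not to ask for them. A site working from the flowsheet alone could finish the study without them, and they cannot be taken later.

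The compliance rules might not reveal the gap. SAP 5.3 takes the expected number of procedures from the flowsheet, so an unscheduled image would never count as missed. With three participants, each lost image set is a third of the data for that outcome, and SAP 4.4 simply excludes missing observations.

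**Working it through.** The plan gives no figure to reproduce here. The check compares the outcome text with the schedule and then asks whether a blank Week 104 cell can be trusted.

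**1. Outcome text.** Protocol 8.2, Protocol 9.2, SAP 3.5.2, SAP 8.2 and SAP Table 7 all place the RCH-size outcomes at Week 104. The four text sections name photography and FA as the source. None disagrees.

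**2. Marks in the flowsheet as read.**

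| Row group | Year-1 marks per row | Extension marks per row (Weeks 60, 72, 84, 104) |
|---|---|---|
| 8 rows tested at every visit | 10 | 4 |
| Refraction, photography, FA | 3 | 0 |
| Four laboratory panels | 2 | 0 |
| History, physical examination, HbA1c | 1 | 0 |

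Seven rows are marked at only some post-baseline visits in year 1 (3 + 4). All seven are empty in the extension.

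**3. A test on rows with a known answer.** SAP 9.6 states that the laboratory tests other than HbA1c also occur at Weeks 16 and 104. The Week 16 marks are in the year-1 table. The Week 104 marks are not in the extension table. The protocol's text gives laboratory timing only for screening and baseline (section 4.2), so the flowsheet is the likely source of the SAP's Week 16 and Week 104 timing. Six of the seven empty rows (photography, FA and four panels) therefore have a Week 104 test stated elsewhere in the documents. A single fault, the loss of a lone mark in the last column, would explain all six.

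**4. Is there a row showing that such marks survive?** The pattern in question is four empty cells followed by one mark at Week 104. Of the 8 marked extension rows, 7 carry five marks (the discretionary-visit column included) and 1, vital signs, carries four. Each Week 104 mark ends an unbroken run. No extension row has the pattern, so nothing shows that it would have been preserved.

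**5. Size if the cells were truly blank.**
- Week 104 image sets without a mark: 3 participants x 2 modalities = 6.
- Of the 7 outcomes in SAP Table 7, 2 (the size outcomes) would lose both named modalities, 2 (exudation and epiretinal change) would keep OCT, and 3 name no modality.
- Protocol 4.5.1 treats as a deviation that "Collectively, participants missed more than 15% of a specific assessment/procedure", with the small-number rule "If total number of items (study visits or study assessments/procedures) expected is less than 16, two or more missed is reportable". If no Week 104 image were taken in anyone, the count per modality would be 0 of 9 as read (3 marks x 3 participants), against 3 of 12 = 25%, which is reportable, with Week 104 marked.
- SAP Table 1 pools all procedures. Leaving out injections, pregnancy tests and discretionary visits, year 1 gives 8 x 10 + 3 x 3 + 4 x 2 + 3 x 1 = 100 and the extension 8 x 4 = 32, so 132 per participant. Adding the two images gives 134. Missing both is 2/134 = 1.5% (6/402 over three participants), far below 15%. Table 1 would not flag them with or without the marks, so this count says nothing about whether the schedule is wrong.

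**The case for a change.** The best case for a real omission is that isolated marks did survive elsewhere. The year-1 table keeps 10 of them after baseline (2 each for refraction, photography and FA, and 4 for the panels), 3 of them in its last column, Week 52. The vital-signs row of the extension keeps an empty first cell before its four marks, so empty cells were not always collapsed. History, physical examination and HbA1c also sit in the extension table with no mark and no stated year-2 test, so an empty row can be intended. If the laboratory cells were also truly blank, SAP 9.6 would be a second mismatch with the same column.

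Part of this stands. A true omission cannot be excluded from the text alone. But the comparison is not like for like. The 10 isolated marks are in a different table, in rows that also carry a baseline mark. One empty cell before four marks is not four empty cells before one. The alternative also requires several Week 104 tests stated elsewhere to have been left out of the same column, where one reading fault would suffice.

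Nor do blank cells mean that no images would be taken. Protocol 9.2 says in plain words when they are taken, in a single-center study with three participants.

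**Conclusion.** The concern does not hold. The outcome sections of both documents agree on Week 104 photography and FA. The only contrary evidence is empty cells in a machine-read table, and SAP 9.6 gives a specific reason to think that marks in that column were lost. What is absent for that reason cannot be counted as absent from the plan.

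This rests on two assumptions: that SAP 9.6 drew its Week 104 laboratory timing from the flowsheet, and that the SAP (written to protocol version 5.0) and the protocol at hand describe the same schedule. Neither can be proved from the text, so the conclusion is that no contradiction is shown, not that the marks are known to exist. A reader with the PDF can settle it by looking at the Week 104 column of Appendix 2.

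Even on the unfavorable reading the effect is small: 6 image sets in three participants, in secondary outcomes that SAP 4.0 and 8.0 treat as exploratory without formal analysis. The Week 52 imaging outcomes and the primary safety outcome are unaffected.
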